This proposal unites neuroimagers, experts in conducting and analyzing human PET studies with behavioral scientists, experts in developing and testing treatments for alcoholism. We will conduct the first-ever *in vivo* PET imaging study of KOR and NTX occupancy in two cohorts of HD (18 FHP and 18 FHN) and relate our imaging findings to FH and alterations of drinking behavior by NTX in the ADP. Through this work, we will advance our understanding of (a) the degree of involvement of the kappa system in reducing drinking in humans by NTX, (b) the contribution of FH to this relationship, and (c) refine the use of a new PET imaging tracer. In so doing, we will inform the development of future targeted pharmacotherapies for alcoholism and lay the groundwork for other important investigations into the KOR/dynorphin system *in vivo*.

Primary (P), Secondary (S), and Auxiliary (A) Specific Aims:

- P1. **Occupancy of KOR by NTX and drinking:** To determine the degree to which occupancy of KORs by a 100 mg/day dose of NTX mediates (influences the strength of) responsivity to NTX treatment in all heavy drinkers. It is expected that KOR occupancy will significantly mediate the relationship between NTX treatment and responsivity. „Responsivity“, measured via ADP, is the change in number of drinks consumed at the baseline ADP vs. NTX ADP.
- P2. **Family History of Alcoholism as a moderator:** To determine whether the relationship between NTX responsivity and occupancy of KOR is different in FHP vs. FHN heavy drinkers.
- P3. To determine if baseline KOR availability differs between heavy drinkers and healthy control socialdrinkers

S1. **Baseline KOR differences**

- a. To determine if baseline levels of KOR differ between FHP and FHN heavy drinkers.
- b. To determine if baseline KOR level is related to either baseline drinking or responsivity to NTX.

S2. **Identify and validate a reference region** (area devoid of specific binding) for our new KOR tracer. A reference region would simplify PET analysis.

S3. **Optimize the scan duration** for clinical populations being imaged with the new KOR tracer.

Shorter scans would increase compliance and decrease discomfort to subjects.

A1. **Relationship to other behavioral measures:** To determine if occupancy of KORs is related to measures of alcohol craving, stimulation or sedation, assessed in the ADP.

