We hypothesize that (1) degree of NTX occupancy of KOR during treatment will be correlated with the degree of responsivity to NTX in all heavy drinkers and (2) FHP heavy drinkers, who respond positively to NTX, will have lower baseline KOR levels when compared with FHN heavy drinkers.

2. **Background:** Describe the background information that led to the plan for this project. Provide references to support the expectation of obtaining useful scientific data.

Alcohol abuse is one of the leading causes of disability in the United States. At present, three medications are approved by the FDA for the treatment of alcohol dependence: disulfiram, naltrexone, and acamprosate. However, the efficacy of these agents ranges from minimal to modest, and they are under-utilized in clinical community settings [6, 7]. There is a pressing need for novel medications that are more effective in reducing alcohol use.

Development of new pharmacotherapeutic approaches to treating alcohol dependence should be based on our understanding of the behavioral and neurochemical mechanisms mediating alcohol drinking, as well the efficacy of agents known to reduce alcohol drinking. Naltrexone (NTX) is a non-specific opioid antagonist that has been shown to have minimal-modest efficacy in treating alcohol dependence. Clinical trials indicate that treatment-seeking heavy drinkers who receive NTX at a dose of 50 mg/day [1, 8] or 100 mg/day [9], have lower levels of relapse to drinking during the treatment period than do those receiving placebo. Subpopulations of alcohol dependent patients may respond better to NTX [10] and family history (FH) of alcoholism is emerging as an important predictor of NTX response [3, 11].

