Primary Aim 1. Occupancy of KOR by NTX and drinking. This aim seeks to determine the degree to which occupancy of kappa by NTX mediates responsivity to NTX in heavy drinkers. Responsivity to NTX is defined as the change in the total number of drinks consumed in the NTX ADP versus the baseline ADP. Tests for mediation will be conducted using the regression strategies described initially Baron and Kenny [53], and the more recent elaboration by Kraemer et al. [54]. The proposed mediator (i.e., the potential mechanism of change), occupancy of KORs, is measured as the fractional change in BP_{ND} before and after treatment with NTX. The analyses will determine whether occupancy is associated with a) NTX treatment, and b) NTX responsivity.

Primary Aim 2. Family History of Alcoholism as a moderator: This aim seeks to determine if the relationship between NTX responsivity and occupancy of KOR is altered by FH status. FHP and FHN will be compared on NTX responsivity and occupancy of KOR. Tests for moderation will be conducted using the strategies described by Baron and Kenny [53], and the elaborated by Kraemer et al. [54]. The primary tests will be whether there is a significant FH by dose interaction on NTX response and occupancy of KOR.

Secondary Aim 1. Baseline KOR differences. This aim seeks to determine if baseline levels of KOR differ between FHP and FHN heavy drinkers, and are related to either drinking in baseline or NTX ADP. FHP and FHN groups will be compared using chi-square tests for categorical variables, and using t-tests or Mann-Whitney tests for continuous variables. All continuous variables will be examined for adherence to the normal distribution using normal probability plots and Kolmogorov-Smirnov tests. If normality is not satisfied and transformations do not help with achieving normality, alternative analytic strategies will be considered such as generalized estimating equations or nonparametric methods. The relationship between baseline KOR and drinking will be examined via Pearson product-moment correlations.

Secondary Aims 2 and 3. Scan duration and reference region. We will look for correlations between BP_{ND} estimates based on 2T model with full AIF and all data vs alternative models and data ranges. Group variances in baseline KOR at or lower than 2T estimates will permit adoption of simpler models.

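### Primary Aim 2 asks whether the occupancy–response relation differs by family history, but its named primary tests compare only group means; Primary Aim 1's mediation label should read association

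*Combined protocol and SAP*

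**What the plan says.** **Primary Aim 2.** The Specific Aims set the question: "To determine whether the relationship between NTX responsivity and occupancy of KOR is different in FHP vs. FHN heavy drinkers". The Primary Aim 2 paragraph under Statistical Considerations repeats it, cites general moderation strategies, and then names the deciding analysis: "The primary tests will be whether there is a significant FH by dose interaction on NTX response and occupancy of KOR". Items a and d of the Research Plan, and the dose justification, give one maintenance dose. Drinking and occupancy are each assessed once off naltrexone (NTX) and once on it.

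**Primary Aim 1.** The wording varies from place to place:
- The Specific Aims say that occupancy "mediates (influences the strength of) responsivity to NTX treatment in all heavy drinkers", and add: "It is expected that KOR occupancy will significantly mediate the relationship between NTX treatment and responsivity".
- Hypothesis 1 is a correlation: "degree of NTX occupancy of KOR during treatment will be correlated with the degree of responsivity to NTX in all heavy drinkers".
- Statistical Considerations says "Tests for mediation will be conducted using the regression strategies" and describes "The proposed mediator (i.e., the potential mechanism of change), occupancy of KORs" as the thing tested. It ends with "The analyses will determine whether occupancy is associated with a) NTX treatment, and b) NTX responsivity".

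Every heavy drinker has a baseline alcohol drinking paradigm (ADP) session and then one on NTX. Healthy controls take no drug (Medication Administration) and do no ADP (Practice ADP session). Item a of the Research Plan explains the lack of placebo, admits possible order effects and aims at an initial signal.

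**Sample size.** The Power analysis covers reduced drinking on NTX and an FH effect of 0.91, and proposes 18 per arm (36 in all). The Research Plan and Targeted Enrollment give 56 heavy drinkers (28 per FH group). No power is given for the occupancy–response association or for its difference by FH.

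**The concern.** P2 is about two slopes: how strongly change in drinks follows occupancy in family-history-positive subjects, and how strongly in family-history-negative subjects. The named tests are about two means. A prespecified primary analysis could therefore report moderation of the occupancy–response relation when that relation is the same in both groups, or report none when it runs in opposite directions. The study's background reports that the two FH groups respond in opposite directions to the same dose, so the distinction is central to its rationale.

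For P1 the stake is the conclusion. A significant result would support an association, while the aim and the analysis paragraph would let it be reported as evidence of mechanism.

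**Working it through.** **1. The plan's own figure.** For effect size 0.91, the Power analysis gives 16 per arm for 80% power. A two-sample noncentral t calculation gives 81% at 16 per arm one-sided and 70% two-sided. At the plan's two-tailed 0.05, power is 76% with 18 per arm and 92% with 28. All of these concern a difference between FH means in drinking, not a difference in slopes.

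**2. What FH by dose tests.** Let D be the change in drinks (NTX minus baseline) and O the occupancy. With only an off/on contrast, the interaction on drinks is

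(NTX − baseline in FH-positive) − (NTX − baseline in FH-negative) = mean D(FH+) − mean D(FH−).

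O is itself a baseline-to-NTX change, so the same interaction on occupancy is mean O(FH+) − mean O(FH−). The P2 question is b3 in

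D = b0 + b1·FH + b2·O + b3·FH·O + error.

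With μ+ and μ− the group means of O, the gap in mean D is b1 + b2(μ+ − μ−) + b3·μ+. It can be large when b3 = 0, and it can vanish when b3 is not 0, for instance when the two lines cross at a common mean occupancy.

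**3. Size.** Assumptions: residual SD 1, occupancy centred with SD 1, equal mean occupancy in the FH groups, two-sided 0.05, 20,000 simulated studies per cell. The documents give none of these inputs. Entries are the percentage significant at 36 / 56 subjects.

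| Truth | FH mean difference in D | FH mean difference in O | FH × occupancy |
|---|---|---|---|
| Slopes +0.5 and −0.5, no mean gap | 5 / 5 | 5 / 5 | about 75 / 93 |
| Equal (zero) slopes, gap 0.91 SD | 76 / 92 | 5 / 5 | 5 / 5 |
| Slopes 0.5 and 0, no mean gap | 5 / 5 | 5 / 5 | about 27 / 43 |
| Slopes +0.3 and −0.3, no mean gap | 5 / 5 | 5 / 5 | about 38 / 56 |

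The 0.91 gap takes the Power analysis figure as an SD difference in response, which is one reading of it.

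**4. Detectable interaction.** On the Fisher z scale, 80% power needs a difference of 2.80 × √(2/(g − 3)) for g subjects per group. For g = 18 this is 2.80 × √(2/15) = 1.02, for example r = +0.47 versus −0.47. For g = 28 it is 2.80 × √(2/25) = 0.79, for example +0.38 versus −0.38.

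**5. P1, step (a).** Occupancy is defined as the change in binding from baseline to NTX, so its association with NTX treatment only asks whether mean occupancy differs from zero. A one-sample t-test has 80% power at 0.48 SD (36) or 0.38 SD (56). For an assumed SD of 10 to 20 percentage points, that is about 5 to 10 or 4 to 8 points.

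**6. P1, step (b).** This relates two pre/post changes across people. Simulation with no NTX effect on drinking and an order effect of 0.5 SD of change (10,000 runs, assumed inputs):
- No shared cause: step (b) is significant in 5% / 5%.
- A shared trait giving correlation 0.3 between occupancy and change: 43% / 62%.

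The common cause produces the false signal; the order effect alone does not.

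**7. Detectable P1 association.** tanh(2.80/√(n − 3)) = 0.45 at n = 36 and 0.37 at n = 56.

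**The case against.** - **The cited moderation strategies could include FH × occupancy.** They could. But the sentence naming the primary tests does not list it, and that sentence fixes the analysis.
- **The FH mean comparisons are worth having.** This stands. They bear on the background finding and should be kept under their own label.
- **P1 is already an association.** This largely stands. Hypothesis 1 and the last sentence of the Primary Aim 1 paragraph say so, which is why only the wording needs correcting.
- **The design's limits are disclosed.** This also stands. The lack of placebo is explained, order effects are admitted, and mock sessions and beverage tasting are meant to lessen them. A reader might infer that order effects alone make a P1 association spurious. Step 6 shows that a shift shared by all subjects does not.
- **Should baseline-adjusted drinks replace the change score in P1?** A reader might infer so from regression to the mean, but the documents do not settle it. With no true occupancy effect, pre–post correlation 0.5 and occupancy correlated 0.3 with baseline drinks (all assumed), there are two cases. If occupancy follows the observed baseline count, the change-score test is falsely significant in 14% / 20% and the adjusted test in about 5%. If it follows a stable drinking level, the change-score test stays at 5% and the adjusted test rises to 18% / 26%. Requiring the two to agree in direction hardly helps in the second case (about 18% to 17%, and 27% to 25%).

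**Conclusion.** The P2 mismatch is an error as written. It follows from the plan's wording and the single maintenance dose. The simulated percentages only illustrate its size and rest on assumed SDs and slopes. The matching test is well powered only for large slope differences, so a null P2 result must not be read as no moderation.

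The P1 point is secondary and a matter of wording. The mediation label exceeds what one sequence without an untreated drinking comparator can show. A reader might go further and conclude that the design is invalid or that P1 will be falsely positive. The documents do not support that: they give no correlation between occupancy and drinking or any shared trait, and the stated test is a legitimate association.

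**What to change.** **P2**
- Replace FH by dose with FH × occupancy on change in drinks as the primary test, and report the slope with its interval in each FH group.
- Keep the FH comparisons of mean responsivity and mean occupancy as separately labelled analyses.
- State the detectable interaction (step 4) and the power for moderate slope differences.

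**P1**
- Replace mediation wording with association in the aim, the analysis paragraph and the conclusions, in line with hypothesis 1. Report step (a) as a binding check.
- Keep the plan's change in drinks as the one prespecified outcome, and show the baseline-adjusted model as a sensitivity analysis.
- Label any model containing the NTX or 6-beta-naltrexol level exploratory. Exposure may drive occupancy, so adjusting for it can remove the variation P1 studies. With an assumed slope of 0.5 and a level–occupancy correlation of 0.7, power falls from 80% to 52% (36) or 94% to 72% (56).
- State the detectable |r|: 0.45 or 0.37.

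**Cost.** Wording and one model term; no new data or visits. The P1 claim becomes weaker and the P2 test harder to pass. P1 and P2 must be reported together: with slopes of +0.5 and −0.5, the pooled occupancy term is significant in only about 7%.

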- d. Dose, Timing of NTX and PK samples: We will taper subjects up to a NTX maintenance dose of 100 mg/day. 100 mg/day is the dose of NTX that has shown efficacy in many recent clinical trials [9], and our own preliminary evidence suggests that this dose may produce the greatest *reduction* in drinking in FHP drinkers but *increased* drinking in FHN drinkers. We considered testing more doses of NTX but we felt that this would not have been justified and would have been too costly. NTX dose will be administered at approximately 10 am each

day. All participants will start with 25 mg/day and be tapered up to 100 mg by day 3 of medication. We will obtain 2 blood samples for pharmacokinetic (PK) analysis during the post PET scan to confirm that steady state levels of NTX were in effect during these procedures. These PK samples will be tested for NTX and its major active metabolite, 6(beta)-naltrexol.

- e. Tobacco Use and Smoking breaks: In our experience, 50% of alcoholics who participate in our projects smoke cigarettes or use other tobacco products. In order to avoid nicotine withdrawal, on the ADP days, participants will be given smoke breaks until about an hour prior to the start of the ADP. We will not allow them to smoke during the ADP since this could not only alter their craving for alcohol but could also pose a potential risk (since YNHH is a nonsmoking facility and the participant would have to be walked out for a smoke break while intoxicated). On the PET days, we will allow regular smoke breaks up until about two hours prior to PET scans. It is very unlikely that the smoking on the morning of the scans would cause kappa receptors to upregulate. Since these individuals have been smoking and drinking regularly, we expect that any receptor regulation from smoking probably happened a long time ago. Further, if there is any acute dynorphin release associated with a smoking break, it will occur sufficiently early relative to the start of the PET scan to minimize any residual effect of transiently elevated dynorphin on our measurements of KOR level (BP_{ND}).

Recruitment:

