PK samples: Two PK samples will be collected during the NTX PET session. Days 5-11 were chosen for the NTX PET scan to build some flexibility into scheduling but maximize the likelihood that NTX levels would be at equilibrium, which will be confirmed by PK analyses. We will also look (on a population basis) for a relationship between occupancy of KOR and NTX (and 6(beta)-naltrexol) levels and interaction with FH of alcoholism.

ROI analysis and parametric image generation: After data reconstruction with all corrections, a new summed image (0-10 min) will be registered to the subject’s T1-weighted MR image, which will be registered to an MR template so that PET and MR images are in the same MNI space. ROI’s, including the 13 examined in the Preliminary data section in Figures 4 and 6 will be taken from a template (Anatomical Automatic Labeling (AAL) for SPM2).

Possible to dispense with arterial sampling, 2T model fitting?: Preliminary results suggest that the

cerebellum may be an appropriate reference region. That is, it may be devoid of KOR. It certainly has low specific binding compared to the other regions assayed. The excellent agreement between BP_{ND} estimated by the 2T model and by SRTM certainly suggests that in healthy controls, we can assess BP_{ND} at baseline with a reference region model using the cerebellum as the reference region. If this turns out to be generally true (e.g., in larger samples, in heavy drinkers), then we can justifiably dispense with arterial sampling and analyze all data via reference tissue models (such as SRTM and SRTM2). As mentioned in Preliminary PET studies, to validate the absence of KOR in the cerebellum, under multiple scan conditions (baseline and NTX) in clinical populations, we will have to show that V_T of cerebellum does not change between baseline and NTX (i.e., there is no specific binding to block).

Possible to shorten scan duration?:

Preliminary results also indicate that we could shorten the scan duration from 2 hrs (used in our preliminary scans) to 1 ½ hrs without any loss of accuracy or precision.

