Auxiliary Aim 1. Kappa and behavioral indicators relevant for alcoholism. This aim will examine the correlations between occupancy of KOR and alcohol craving, stimulation and sedation. A series of Spearman rank-order and Pearson correlation analyses will be conducted for this aim.

Power analysis: The sample size was based on the power calculations for the hypotheses of (a) reduced drinking in the NTX 100 condition, and (b) power to detect an interaction by FH. Power calculations were generated using G*Power software Version 3.0 [55]. Effect sizes were estimated based on the preliminary FH and NTX effects on drinking behavior in the ADP described in [6] and in our preliminary studies. The effect size for the effect of FH is .91. To detect this effect size at $\alpha=.05$ with 80% power, a total of 16 participants would be required for each arm. Therefore the proposed sample size of $n=18$ per arm would be sufficient to detect differences in drinking between FHP and FHN at the 100 mg dose of naltrexone.

SECTION VI: RESEARCH INVOLVING DRUGS, DEVICES, BIOLOGICS & PLACEBOS

Are there any investigational devices used or investigational procedures performed in a YNHH Operating Room? Yes No *If Yes, please be aware of the following requirements:*

- a. A YNHH OR New Product/Trial Request Form must be completed. Please contact the OR Materials Manager, [name], at [contact] for more information on this requirement;
- b. Your request must be reviewed and approved by the Operating Room New Technology Committee before patients may be scheduled; and
- c. The notice of approval from the OR New Technology Committee must be submitted to the HIC for the protocol file.

1. **Identification of Drug, Device or Biologic:** What is (are) the **name(s)** of the drug(s), device(s) or biologic(s) being used? Identify whether FDA approval has been granted and for what indication(s).
Naltrexone is an FDA approved drug that is used in the treatment of alcoholism and opioid addiction.
[C-11]LY2795050 ([C-11]PKAB) PET radiotracer to image kappa opioid receptor, Production of [C-11]LY2795050 ([C-11]PKAB) will be performed with the permission of Yale-New Haven Hospital RDRC

All protocols which utilize a drug, device or biologic **not** approved by, but regulated by, the FDA must provide the following information: **Not applicable to this research project**

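### The primary test named for Aim 2 compares family-history group means; it does not test whether family history changes the occupancy–responsivity relationship

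*Combined protocol and SAP*

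**What the plan says.** Specific Aims, P2, sets the question: "To determine whether the relationship between NTX responsivity and occupancy of KOR is different in FHP vs. FHN heavy drinkers". Statistical Considerations, Primary Aim 2, repeats it: "This aim seeks to determine if the relationship between NTX responsivity and occupancy of KOR is altered by FH status".

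The same paragraph then describes the analysis. First: "FHP and FHN will be compared on NTX responsivity and occupancy of KOR". It next cites two general moderation frameworks without writing a model, and ends: "The primary tests will be whether there is a significant FH by dose interaction on NTX response and occupancy of KOR".

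Four other places bear on how that test can be read:

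- **Primary Aim 1, outcome.** "Responsivity to NTX is defined as the change in the total number of drinks consumed in the NTX ADP versus the baseline ADP". Occupancy is likewise defined there as a fractional change in BP_ND from before to after NTX.
- **Research Plan, item d (Dose, Timing of NTX and PK samples).** Subjects are stepped up to a single maintenance dose: "We considered testing more doses of NTX but we felt that this would not have been justified and would have been too costly".
- **Power analysis.** The sample size is described as "sufficient to detect differences in drinking between FHP and FHN at the 100 mg dose of naltrexone".
- **PET Methods, ROI analysis.** Occupancy can be computed in many regions, "including the 13 examined in the Preliminary data section in Figures 4 and 6 will be taken from a template".

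**The concern.** The aim concerns a slope: does occupancy predict change in drinking differently in the two family-history groups? The test designated as primary treats response and occupancy as two separate outcomes and relates neither to the other.

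This can mislead in three ways. The test can be positive when family history has no bearing on the occupancy–responsivity link. It can miss a real slope difference when group means are similar. When a slope difference does shift the means, the test cannot tell that apart from a plain mean difference.

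The first is the most serious here. The Specific Aims and Background report an earlier FHP/FHN difference in drinking on this dose, and the sample size is built on it. Replicating that difference alone would probably make the named test positive. Nor does the plan say whether one or both outcomes must be significant.

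**Working it through.** **1. What the named test estimates.** Let D be drinks and g the FH group. With conditions baseline (0) and NTX (1), the FH × condition interaction on drinks is

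[mean D₁ − mean D₀] in FHP − [mean D₁ − mean D₀] in FHN = mean responsivity in FHP − mean responsivity in FHN.

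Occupancy is one change score per subject, so the same step gives the FHP − FHN difference in mean occupancy (or FH × condition on BP_ND). Neither contains a slope of responsivity on occupancy. The only FH interaction involving occupancy elsewhere (PET Methods, PK samples) concerns drug and metabolite levels, not drinking.

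**2. The plan's own power figure.** Inputs from the Power analysis: effect size 0.91, alpha 0.05, 80% power, 16 per arm. Statistical Considerations specifies two-tailed tests. For a two-sample t-test with noncentrality 0.91 × √(n/2):

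| n per group | one-sided power | two-sided power |
|---|---|---|
| 16 | 80.8% | 70.2% |
| 18 | 84.9% | 75.6% |
| 20 | 88.1% | 80.1% |
| 28 | 95.7% | 91.7% |

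The stated 16 is reproduced only as a one-sided test. In either case the calculation covers a difference in mean drinking. Both 18 per group (overview before the Specific Aims; Power analysis) and 28 per group (56 heavy drinkers in the Research Plan, split equally) are carried forward, because the documents give both.

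**3. Named test against slope test.** Simulation with 20,000 replicates per scenario, standardised variables and two-sided 0.05. The comparison is pooled t-tests against the product term in `responsivity ~ occupancy + FH + occupancy × FH`, fitted by ordinary least squares. Slopes and the occupancy mean/SD ratio are assumptions.

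| Scenario | Response test, 18 / 28 | Occupancy × FH, 18 / 28 |
|---|---|---|
| (i) Mean responsivity differs by 0.91 SD, no slopes, equal mean occupancy | 76% / 92% | 5% / 5% |
| (i′) As (i), common slope r = 0.5 | 75% / 92% | 5% / 5% |
| (ii) Slopes +0.5 and −0.5, equal means | 5% / 5% | about 87% / 97% |
| (iii) Slopes as (ii) from a shared zero-occupancy origin, occupancy mean/SD = 0.5 | 31% / 46% | 86–87% / 97–98% |
| (iii) mean/SD = 1 | 83% / 96% | 86–87% / 97–98% |
| (iii) mean/SD = 2 | 100% / 100% | 86–87% / 97–98% |

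In (iii) the induced mean difference in SD units is (0.5 + 0.5) × mean/SD, that is 0.5, 1 and 2. The named test's power therefore follows that ratio and not the slope contrast, which is the same in all three rows.

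**4. The missing and/or rule.** In (i) the two outcomes are independent and occupancy is null.

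- Either significant: 1 − (1 − 0.756) × 0.95 = 77% at 18 per group; 1 − (1 − 0.917) × 0.95 = 92% at 28.
- Both significant: 0.756 × 0.05 = 3.8%; 0.917 × 0.05 = 4.6%.

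**5. What a slope test can detect.** By Fisher z, 80% power needs q = (1.960 + 0.842) × √(2/(n − 3)).

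- n = 18: q = 2.80 × √(2/15) = 1.02. Opposite correlations: tanh(q/2) = ±0.47. One group only: tanh(q) = 0.77.
- n = 28: q = 2.80 × √(2/25) = 0.79. Opposite correlations: ±0.38. One group only: 0.66.

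Least squares at ±0.47 and ±0.38 gave 81% power in both cases. For an association in one group only, with equal total variances, least squares gives 74% at r = 0.80 with 18 per group, and 80% at r = 0.70 with 28 per group.

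**The case against.** - **The slope test may have been intended.** The paragraph is headed as a moderation aim and cites frameworks that can include a product term. Intent is plausible. But no occupancy × FH term is written, and the plan designates something else as primary. An analyst following the text would run the mean comparisons.
- **Reading dose as baseline versus NTX repairs an unclear sentence.** True. It is also the only reading under which the term can be estimated, so the alternative is that Aim 2 has no usable primary test.
- **The group comparisons have a purpose.** The Background does set out to compare occupancy between FHP and FHN drinkers. This is a reason to keep them as secondary analyses; they still do not answer P2.
- **A missed slope difference is unlikely on the trial's own premise.** This has weight. Scenario (ii) needs lines that cross at mean occupancy, while the sponsor expects opposite mean responses. The low-power case in (iii), mean/SD = 0.5, implies under normality about 31% of treated subjects with negative occupancy. The main harm is therefore misattribution.
- **The detectable one-group correlation depends on the model.** This stands. At r = 0.80 and 18 per group, power is 74% with equal total variances, 85% by Fisher z and 94% with equal residual variances.
- **This is a small mechanistic study seeking an initial signal.** It is, but Aim 2 is one of its primary aims and the remedy is a few sentences.

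**Conclusion.** The concern holds. As written, no stated test answers primary Aim 2. The algebra in step 1 needs only the plan's own definitions and a baseline-versus-NTX reading of dose.

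The size of the problem rests on assumed slopes, normal standardised variables and the plan's 0.91 read as a standardised mean difference in responsivity. On those terms the named response test is positive in 76% (18 per group) or 92% (28 per group) of trials in which family history does not alter the slope, against 5% for the correct test. It can also miss a slope difference, but that depends on the configuration and is less likely given what the sponsor expects. This should be corrected before the data are analysed.

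**What to change.** Replace the primary-test sentence with wording such as: *The primary test for Aim 2 is the two-sided 0.05 test of the occupancy × FH coefficient in a linear model for responsivity (change in drinks, as defined in Aim 1) with occupancy, FH and occupancy × FH, using one prespecified occupancy region or summary.*

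In addition:

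- State in advance whether baseline-session drinks enter as a covariate.
- Report the FH differences in mean response and mean occupancy as secondary.
- Say that the 0.91 calculation covers a group difference in drinking, not this test, and give the detectable slope contrast with its variance assumption.

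A single occupancy measure matters. Testing the product term at 0.05 in each of 13 regions under the null gives at least one significant result in 15% to 42% of trials at 18 per group, and 14% to 43% at 28, for assumed inter-region correlations from 0.9 down to 0.3.

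The cost is wording only, since every variable is already collected. The drawback is a less favourable statement of sensitivity: 80% power needs opposite correlations of about ±0.47 at 18 per group or ±0.38 at 28. If only one group shows an association, the correlation must be about 0.66 to 0.70 at 28 per group. At 18 per group it is about 0.77 by Fisher z and above 0.80 by least squares with equal total variances.
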